### **Non Hematologic:**

Any ≥ Grade 4 non-hematologic toxicity will be considered a DLT.

Any non-Hy's law ≥ Grade 3 liver abnormality is a DLT unless it resolves within 72 hours.

Any ≥ Grade 3 infection lasting more than 7 days in the absence of active AML is considered a DLT.

Any ≥ Grade 3 bleeding with thrombocytopenia in the absence of active AML is considered a DLT.

Any ≥ grade 3 non-hematologic toxicity not resulting directly from active leukemia is a DLT, with the exceptions of:

- Alopecia
- Line associated venous thrombosis
- Grade 3 fatigue, anorexia, constipation
- Grade 3 or 4 electrolyte disturbance that resolves within 24 hours with electrolyte correction and is not clinically significant,
- Grade 3 nausea or vomiting that does not require hospitalization or support with total parenteral nutrition and resolves to < grade 2 within 72 hours

The DLT observation period is defined as cycle 1 day 1 until completion of cycle 1 and will require that in the absence of DLT, patients receive at least 14 of the 21 planned doses of TP-0903 during cycle 1 to be considered evaluable for the tolerability check of the phase 1b. In other words, a patient will be considered unevaluable for the tolerability check and phase 1b component if a patient does not complete the DLT observation period due to reasons other than toxicity (e.g. progression). These patients will still be considered evaluable and included in the denominator when analyzing efficacy endpoints.

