#### **Hematologic toxicity:**

Any ≥ Grade 4 neutropenia lasting more than 14 days past the end of the cycle (by day 42) in the absence of active AML should be considered DLT. For patients with > 5% blasts, myelodysplastic changes, or evidence of disease by flow cytometry/cytogenetics, failure to recover normal neutrophil count will not be considered DLT as this could be the result of persistent disease. Any patients who stop treatment prior to completing evaluation for the DLT observation period due to disease progression or refusal for further participation for reasons other than toxicity will be replaced for the purposes of dose- finding and safety evaluations.

Other events may occur which do not meet the definition of a DLT but are concerning to the investigators and sponsor and may be then considered to be DLTs. Any other toxicities occurring during subsequent cycles after cycle 1 will lead to dose modifications as specified below. The National Cancer Institute Common Terminology Criteria for Adverse Events (CTCAE) version 5.0 (<http://ctep.cancer.gov>) will be used to characterize toxicities.

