### Confirmation of Tolerability

TP-0903 monotherapy has been evaluated in solid tumors and found to be safe at a dose level of 50 mg daily. Although we do not anticipate any safety challenges in patients with AML at this dose level, an early tolerability assessment will be included for the first 6 patients enrolled based on a standard Rolling 6 design. If at most one in 6 patients has a DLT (See Section 4), then TP-0903 monotherapy at 50 mg daily will be considered safe and we will proceed with full accrual of the phase 2 study. If however TP-0903 monotherapy at 50 mg daily does not have acceptable toxicity in the first 6 patients, then an additional 6 patients will be treated at a lower dose level of TP-0903 at 37 mg daily, and the same rule will be used to confirm tolerability. Once a tolerable dose level is confirmed, enrollment can continue to the phase 2 component at that dose level.

### Phase 2

At the confirmed tolerable dose level, TP-0903 monotherapy will be assessed for efficacy in a phase 2 component. Efficacy data from patients treated at the confirmed tolerable dose level during the tolerability check will be utilized in the phase 2 portion of the trial. Efficacy will be assessed using Simon's optimal two-stage phase 2 clinical trial design constraining type I and II errors to 10%.

The primary endpoint is the composite CR rate (CR/CRh), defined according to the 2017 ELN AML Recommendation. All eligible patients who start therapy will be considered evaluable for the primary endpoint and included in the denominator when calculating the composite CR rate. In relapsed/refractory adult patients with AML and FLT3 mutations, the ADMIRAL phase 3 study reported a composite CR rate of 34% with the FLT3 inhibitor gilteritinib, which led to improved overall survival (REF). We will therefore test the null hypothesis that the composite CR rate with TP-0903 is 30% versus the alternative hypothesis that it is 55%. By design, if 13 or more of 31 evaluable patients achieve CR/CRh, then there will be sufficient evidence to warrant further study of TP-0903 in this patient population. An interim analysis will occur after 13 patients have response determined. If 4 or fewer of 13 evaluable patients achieve CR/CRh, then the study will be terminated early. If 5 or more of 13 evaluable patients achieve CR/CRh then enrollment will continue as planned for all 31 evaluable patients. The probability of early termination under the null hypothesis is 0.65.

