Toxicity will continue to be monitored throughout the phase 2 component, and a rule for excessive toxicity will be continuously applied. The monitoring rule will be evaluated during the first cycle of

therapy and will be based on the number of patients with a DLT out of the total number of patients treated (See Table Below). The number of patients with a DLT that would warrant accrual suspension corresponds to a high posterior probability that the true DLT probability is greater than an acceptable level (i.e.,  $\Pr(p_i > 0.25 | \text{data}) > 0.95$ ), where the posterior probability is determined from a *Beta-Binomial* distribution with *Beta* (1, 1) as the prior on  $p_i$ . For example, if 9 patients have been treated in the phase 2 study, and 5 or more patients have a DLT, then this is sufficient evidence of excessive toxicity and accrual will be suspended while data are reviewed more closely, and a decision will be made to modify or close the study.

**Table:** Excessive Toxicity Rule, following the Confirmation of Tolerability in the First 6 Patients

Number of Patients	7	8	9	10	11	12	13	14	15	16
Number with DLT	4	4	5	5	6	6	6	7	7	7
Number of Patients	17	18	19	20	21	22	23	24	25	26
Number with DLT	8	8	8	9	9	9	10	10	10	11
Number of Patients	27	28	29	30	31					
Number with DLT	11	11	12	12	12					

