### Accrual

In the phase 1b component, we expect 6 patients and a maximum of 12 patients. In the phase 2 component, we will over-accrue by roughly 10% and target an accrual of 34 patients. Overall, we plan to accrue 40-46 patients. Based on past accrual of FLT3-mutated AML patients at OSU, we would anticipate accruing 1-2 patients per month, with accrual completed in 2-3 years.

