### Analysis of Secondary Endpoints

The degree of response will be summarized. Among eligible patients who achieve CR/CRh, disease-free survival (DFS) will be calculated. DFS is defined from the date of first CR/CRh until the first date of relapse/progression or death from any cause. Any patient without progression or death will be censored at the last date of clinical assessment. Further, patients who go to transplant prior to a progression will be censored at that time. The number and proportion of patients going to transplant prior to progression will be provided. Overall survival (OS) will be calculated for all eligible patients who start therapy. OS will be defined from the treatment start date until the date of death from any cause or date last known alive. Both time-to-event endpoints will be summarized by the Kaplan-Meier method. Associations between baseline variables and clinical outcome will be descriptive in nature due to the small sample sizes, primarily using

graphical displays to identify patterns and trends.

The maximum grade of each type of adverse event will be recorded for each patient and summarized. Treatment-related adverse events, defined as possibly, probably or definitely related to study treatment per NCI CTCAE v5.0 will be summarized separately. In addition, reasons for treatment discontinuation and number of TP-0903 cycles received will be summarized and used to assess tolerability. All patients who have received at least one dose of study drug will be evaluable for safety and tolerability assessments.

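### The phase 2 excessive-toxicity rule counts all treated patients, so non-toxicity leavers from cycle 1 enter as full non-events; the printed table should be entered with DLT-evaluable patients

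*Combined protocol and SAP*

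**What the plan says.** **The rule.** Section 10, Phase 2, states that "a rule for excessive toxicity will be continuously applied". It is "based on the number of patients with a DLT out of the total number of patients treated". Accrual is suspended when Pr(p > 0.25 | data) > 0.95 under a Beta(1, 1) prior. A table gives the boundary for 7 to 31 patients. The worked example counts in the same way: "if 9 patients have been treated in the phase 2 study, and 5 or more patients have a DLT".

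**Early leavers.** Section 4.1 requires a patient without a DLT to have received at least 14 of the 21 planned doses in cycle 1. Otherwise, where the reason is not toxicity, "a patient will be considered unevaluable for the tolerability check and phase 1b component". The hematologic part of Section 4.1 adds that patients who stop before the observation period is complete, because of progression or refusal unrelated to toxicity, "will be replaced for the purposes of dose- finding and safety evaluations".

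**Safety set.** Section 10, Analysis of Secondary Endpoints, states: "All patients who have received at least one dose of study drug will be evaluable for safety and tolerability assessments".

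**Follow-up after stopping.** Section 5.3.1 keeps adverse event reporting open for 30 days after the drug is discontinued.

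**The concern.** A patient who progresses and stops in the first days of cycle 1 has had little exposure over the DLT period. Section 4.1 treats that patient as uninformative about DLT in phase 1b. The phase 2 rule gives the same patient as much weight as one who finished the cycle without a DLT. Each such patient pulls the posterior down.

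Accrual can therefore continue when the patients who can be assessed already meet the plan's own 0.95 standard. This table is the only numerical suspension rule for toxicity in phase 2. Early exit is also foreseeable in relapsed/refractory AML: Section 4.1 names progression as a reason and writes rules for it.

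**Working it through.** **1. The plan's own table.** With x DLTs among n patients, the posterior is Beta(1+x, 1+n−x). For whole numbers this gives Pr(p > 0.25 | x, n) = Pr(Binomial(n+1, 0.25) ≤ x). Taking the smallest x with a value above 0.95 for n = 7 to 31 reproduces all 25 printed boundaries: 4, 4, 5, 5, 6, 6, 6, 7, 7, 7, 8, 8, 8, 9, 9, 9, 10, 10, 10, 11, 11, 11, 12, 12, 12. The table is right for fully observed patients.

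**2. What the denominator does at the boundary.**

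| DLTs / n | Posterior | Action |
|---|---|---|
| 4 / 8 | 0.951 | suspend |
| 4 / 9 | 0.922 | continue |
| 7 / 20 treated | 0.870 | continue |
| 7 / 16 (4 of the 20 unevaluable) | 0.960 | suspend |

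**3. Chance that the rule fires.**
- From Section 10: at most 1 DLT in the first 6 to proceed; the table applies from patient 7 to patient 31.
- Assumed: true DLT rate p = 0.40; each patient from the 7th on leaves early without a DLT with probability q = 0.10 or 0.20; leavers carry no DLT risk; the first 6 are all evaluable and are pooled into the table.

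Passing the first check has probability 0.6⁶ + 6 × 0.4 × 0.6⁵ = 0.047 + 0.187 = 0.233. From there I used an exact patient-by-patient recursion. A leaver adds 1 to n under the all-treated count and 0 under the evaluable count. Otherwise n rises by 1, and x rises by 1 with probability p.

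Suspension by 31 treated, given that the first check was passed:

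| q | All treated | Evaluable only | Difference | Difference × 0.233 |
|---|---|---|---|---|
| 0 | 0.469 | 0.469 | 0 | 0 |
| 0.10 | 0.321 | 0.416 | 0.095 | 0.022 |
| 0.20 | 0.195 | 0.370 | 0.175 | 0.041 |

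The fair comparison is across a row. The fall from 0.469 to 0.370 at q = 0.20 is information lost to drop-out, which no denominator recovers. Only the step from 0.370 to 0.195 comes from the counting rule.

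**4. When the loss occurs.** With the first 6 pooled and at most 1 DLT among them, the rule cannot fire before patient 10, where it needs 5 DLTs. By patient 13, at q = 0.20, the probabilities are 0.034 (all treated) and 0.041 (evaluable), a gap of 0.007 out of 0.175. About 96% of the loss is therefore later. If phase 2 counts restart from zero, the figures at q = 0.20 are 0.303 and 0.442 by patient 13, and 0.460 and 0.698 by patient 31. The loss after patient 13 is then about 0.099 of 0.238, or 41%. At q = 0.10 it is 39%.

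**5. Cost at the acceptable 25% rate.** At q = 0.20 with no DLT risk in leavers, suspension by 31 treated is 0.015 (all treated) and 0.041 (evaluable). With complete follow-up it is 0.051.

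**The case against.** **The denominator may be deliberate.** Section 4.1 limits its unevaluable status to the tolerability check and phase 1b, and the one-dose safety set in Section 10 agrees with an all-treated count. An evaluable set for dose confirmation and an all-treated set for phase 2 monitoring can coexist. This stands in part: a reader might infer a flat contradiction between Sections 4.1 and 10, and the text does not show one. The tension is with the replacement clause, which covers safety evaluations and can be read as reaching phase 2. Replacing a patient, however, does not remove that patient from the number treated. The one-dose set appears under secondary analyses and does not address the DLT posterior.

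**Leavers are still followed.** A reader might infer that they are lost to safety observation. Section 5.3.1 rules that out for surviving patients, and Section 9 sets an end-of-treatment visit 30 to 37 days after the last dose. Section 4.1 also makes any adverse reaction leading to withdrawal a DLT. What is incomplete is exposure over the DLT period, and that is what the 14-dose condition measures.

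**The effect is small.** A crossing only suspends accrual for review. DLTs and serious events are also discussed at weekly and twice-monthly meetings (Section 5.8). The 6-patient check stops most trials with a high DLT rate. With pooling, nearly all of the gain also needs the second efficacy stage to open ("If 5 or more of 13 evaluable patients achieve CR/CRh then enrollment will continue as planned for all 31 evaluable patients"), which has probability 0.35 at a 30% CR/CRh rate and 0.93 at 55%. All of this stands and limits the weight of the point.

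**Conclusion.** The point holds in a limited form. As written, a non-toxicity leaver without a DLT is a full non-event in phase 2, and the plan's 0.95 standard can be met among evaluable patients while accrual continues. Under the assumptions shown, suspension by 31 treated is 0.32–0.20 instead of 0.42–0.37. Unconditionally that is about 2–4 percentage points at a true 40% DLT rate.

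The size rests on an assumed 10–20% drop-out; with none there is no loss. The only attrition allowance in the plan is "we will over-accrue by roughly 10% and target an accrual of 34 patients", which is not a DLT figure.

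Two stronger readings are not supported:
- That the table is wrong. It reproduces exactly.
- That the loss necessarily falls in the second stage. This depends on pooling the first 6. The table's title and its 7-to-31 range favor pooling. The worked example's reference to patients treated in phase 2, and the accrual sum of 6 + 34 = 40, leave room for a restart. In that case only about 40% of the loss comes after patient 13.

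**What to change.** Keep the prior, the 0.95 threshold and the printed table. In Section 10:

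- Enter the table with DLT-evaluable patients: those with a DLT, plus those without a DLT who completed the observation period with at least 14 of 21 doses, as Section 4.1 already defines.
- State whether the first 6 patients are pooled into the phase 2 count.
- Reconcile the evaluability and replacement clauses of Section 4.1, the phase 2 rule and the one-dose safety set on who is in the phase 2 DLT denominator.

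This takes a few sentences, no extra patients and no new table. The cost is more suspensions at the acceptable 25% rate. At 20% drop-out the rate is about 0.04 instead of 0.015 if leavers carry no DLT risk. In a simulation at 1–2 patients per month with DLT and drop-out times uniform over cycle 1, it is 0.07–0.08 instead of about 0.02. It reaches about 0.10 if DLTs come early in the cycle. These figures should be reported with the rule.

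Time-weighting partly observed patients is optional. If used, the weight must be defined by time on treatment, because adverse event reporting continues after the drug stops.

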### Accrual

In the phase 1b component, we expect 6 patients and a maximum of 12 patients. In the phase 2 component, we will over-accrue by roughly 10% and target an accrual of 34 patients. Overall, we plan to accrue 40-46 patients. Based on past accrual of FLT3-mutated AML patients at OSU, we would anticipate accruing 1-2 patients per month, with accrual completed in 2-3 years.

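### Phase 2 targets 34 patients and counts every eligible patient who starts therapy, but the final decision rule is written only for 31, so 32 to 34 evaluable patients would have no valid success bound

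*Combined protocol and SAP*

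**What the plan says.** All the relevant text is in Section 10 of the combined protocol and SAP, with one supporting sentence in Section 4.1.

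- **Design (Phase 2).** Simon's optimal two-stage design, null CR/CRh rate 30%, alternative 55%, type I and type II errors each limited to 10%. The stated probability of early termination under the null is 0.65.
- **Interim rule (Phase 2).** "If 4 or fewer of 13 evaluable patients achieve CR/CRh, then the study will be terminated early". With 5 or more responders, "then enrollment will continue as planned for all 31 evaluable patients".
- **Final rule (Phase 2).** "if 13 or more of 31 evaluable patients achieve CR/CRh, then there will be sufficient evidence to warrant further study". No other final bound is given.
- **Denominator (Phase 2).** "All eligible patients who start therapy will be considered evaluable for the primary endpoint and included in the denominator". Section 4.1 adds that patients who are unevaluable for the tolerability check still count for efficacy.
- **Accrual.** "In the phase 2 component, we will over-accrue by roughly 10% and target an accrual of 34 patients". The paragraph does not say what the over-accrual is for, whether enrolment stops at 31 evaluable patients, or which patients enter the test if more than 31 are evaluable.
- **Toxicity monitoring.** The table headed "Excessive Toxicity Rule, following the Confirmation of Tolerability in the First 6 Patients" runs from 7 to 31 patients. The posterior rule behind it is written out in the text above it.

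**The concern.** Over-accrual normally replaces patients who drop out of the denominator. This plan's definition leaves only two ways out: being ineligible, or never starting therapy. Early progression, early death and a missing marrow assessment all stay in. If fewer than 3 of the 34 are lost in those two ways, 32, 33 or 34 patients are evaluable and the plan has no rule for them.

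The matter bears on the primary go/no-go decision. With more than 31 evaluable patients, the team would have to choose between keeping 13, raising the bound, or testing a subset of 31. That choice would be made in a single-arm, open study after responses are known. The result could turn on it: 13 responders among 34 is a success if the bound stays at 13 and a failure if it is raised to 14.

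**Working it through.** **Inputs (Section 10).** n1 = 13, stop if 4 or fewer respond; final n = 31, success if 13 or more respond; p0 = 0.30, p1 = 0.55; accrual target 34. The loss rate (ineligible or never started) is not in the documents, so it is varied as an assumption.

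**Formula.** With b(x; 13, p) the binomial probability of x responders in stage 1, total n and bound c:

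P(success) = Σ from x = 5 to 13 of b(x; 13, p) × P(Bin(n − 13, p) ≥ c − x)

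**Step 1: reproduce the plan.** The early-termination probability under the null is P(Bin(13, 0.30) ≤ 4) = 0.6543, against the stated 0.65. Type I error, with c = 13 and p = 0.30 (products taken from unrounded factors):

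| x in stage 1 | b(x; 13, 0.30) | P(Bin(18) ≥ 13 − x) | product, n = 31 | P(Bin(21) ≥ 13 − x) | product, n = 34 |
|---|---|---|---|---|---|
| 5 | 0.1803 | 0.1407 | 0.0254 | 0.2770 | 0.0499 |
| 6 | 0.1030 | 0.2783 | 0.0287 | 0.4495 | 0.0463 |
| 7 | 0.0442 | 0.4656 | 0.0206 | 0.6373 | 0.0281 |
| 8 | 0.0142 | 0.6673 | 0.0095 | 0.8016 | 0.0114 |
| 9 | 0.0034 | 0.8354 | 0.0028 | 0.9144 | 0.0031 |
| 10 or more | | | 0.0006 | | 0.0006 |
| **Sum** | | | **0.0875** | | **0.1395** |

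At n = 31 the power at 0.55 is 0.9016. A full search over two-stage designs meeting both limits returns this same design as optimal, with expected sample size 19.2 under the null.

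**Step 2: more than 31 evaluable patients, interim rule unchanged.**

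| n | Type I error, bound 13 | Power, bound 13 | Type I error, bound 14 | Power, bound 14 |
|---|---|---|---|---|
| 31 | 0.0875 | 0.902 | | |
| 32 | 0.1042 | 0.912 | 0.0591 | 0.8846 |
| 33 | 0.1217 | 0.918 | 0.0726 | 0.8995 |
| 34 | 0.1395 | 0.923 | 0.0874 | 0.9098 |

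Keeping 13 exceeds the 10% limit at all three larger sizes. Raising it to 14 meets both limits only at 34; at 32, and by a hair at 33, no bound meets both.

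**Step 3: how likely is more than 31?** With 34 registered and loss rate q, the chance is P(Bin(34, 1 − q) ≥ 32). At q = 5%: 0.95^34 + 34 × 0.05 × 0.95^33 + 561 × 0.05² × 0.95^32 = 0.175 + 0.313 + 0.272 = 0.76. In the same way it is 1.00 at 0%, 0.97 at 2% and 0.33 at 10%.

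**Step 4: averaged over the number attained.** If 13 were applied to whatever number resulted from 34 registrations, type I error would be Σ P(n evaluable) × P(success | n, c = 13, p = 0.30): 0.1395 at 0% loss, 0.110 at 5%, 0.093 at 8% and 0.083 at 10%.

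**Step 5: toxicity table.** The stated rule suspends accrual at the smallest k with Pr(p > 0.25) > 0.95 under Beta(1 + k, 1 + n − k). It reproduces every printed entry from 7 to 31. Beyond that:

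- n = 32: 12 (0.9516; 11 gives 0.9013)
- n = 33: 13 (0.9719; 12 gives 0.9390)
- n = 34: 13 (0.9637; 12 gives 0.9244)

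**The case against.** The best defence is that the plan ties its rule to 31 twice: once in the success bound and once in saying how far enrolment continues. On that reading 34 is only a registration allowance, accrual stops when 31 are evaluable, and type I error stays at 0.0875. Stopping there is practicable, because evaluability is known once therapy starts and only 1 to 2 patients are expected per month. Losses can also absorb the surplus: at 10% loss the expected evaluable number is 34 × 0.90 = 30.6.

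Much of this stands, and it rules out three stronger readings.

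- A reader might infer that the plan breaks its own type I error limit. It does not: no sentence applies 13 to 32, 33 or 34 patients, and at 8% or 10% loss even that practice would average below 10%.
- A reader might infer that patients 32 to 34 have no toxicity boundary. They do: the posterior rule is stated in full, and the table only lists its values.
- A reader might add the 6 tolerability patients to the 34 and test 13 of 40, which gives 0.238. The Accrual paragraph does add the two components for the overall total, and the Phase 2 text reuses efficacy data from tolerability patients at the confirmed dose. Neither says that 40 patients enter the test.

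What the defence does not supply is the missing sentence. The Accrual paragraph calls 34 a target and mentions no stop at 31, while the denominator sentence, read literally, leaves no ground for excluding the 32nd eligible patient who starts therapy.

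**Conclusion.** The concern holds as an unspecified decision rule. The accrual target, the denominator definition and the final bound do not fit together, and nothing in the plan says which gives way when more than 31 patients are evaluable.

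The consequence depends on two assumptions that the documents do not settle: how many of the 34 are lost, and what the team would then do. With fewer than 3 lost and the bound kept at 13, the false-positive risk is only slightly over the limit at 32, but at 34 it is about 1.6 times the designed value (0.1395 / 0.0875). With 3 or more lost, the question does not arise.

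This is a cheap correction to the primary decision rule and should be made before the data can influence it. It is not an error in the Simon design. The short toxicity table is a minor matter.

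**What to change.** **Preferred.** Add to the Phase 2 text of Section 10 that the interim and final decision rules use the first 13 and the first 31 evaluable patients in registration order, counting tolerability-check patients treated at the confirmed dose. Any further evaluable patients contribute only to the estimated CR/CRh rate and its interval. Type I error stays at 0.0875 and power at 0.902, whatever number is finally enrolled. The same sentence settles the test set if the 6 tolerability patients lie outside the 34.

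**Alternative, if all evaluable patients are to enter the test.** Prespecify 14 or more for 32, 33 or 34 (type I error 0.059, 0.073, 0.087) and restate power as 0.885, 0.8995 and 0.910. This gives up the 90% power requirement at 32 and, marginally, at 33. It also requires stating that no more than 34 patients can enter the test.

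**Minor.** Extend the printed toxicity table by the rule already stated: 12 of 32, 13 of 33, 13 of 34.

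**Cost.** Two sentences and three table entries. No extra patients, and no loss of power under the preferred wording.
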